Sample size	
The sample size for the study was determined to be 240 patients.
 
Calculations were made using two instruments that provided two approximate sample sizes. The median of these values (considering that the better the odds ratio could be achieved from the larger the sample size) was taken as the sample size.
 
(1) Calculate the sample size for scientific studies using a standard numerator based on the proportion of the population that is likely to have the demographic characteristics of the study sample and the size (number) of the population with the clinical characteristics expected for the study, with a 95% confidence level and a <math>\pm 5\%</math> confidence interval for the results of the statistical calculations.

	
(2) Sample size calculation for a randomized, parallel case-control study with a two-sided statistical significance level, at a confidence interval of <math>\alpha = 0.05</math>, at statistical power of <math>(1-\beta) = 0.8</math>, at case/control ratio of 2, at probability of occurrence of an event in the experimental arm of <math>p_0</math> – up to 0.4, and at probability of occurrence of an event in the control arm of <math>p_1</math> – up to 0.6.

Data processing	
The study data will be processed in stages when:
 
I - More than 50% of patients are enrolled in the study;
 
II - The study group is fully formed, and by this time, more than 50% of patients have completed the 3-month observation period, and some patients have completed the 6-month observation period.
 
III - all patients included in the study have completed the 6 months, and some have completed the 12 months;
 
IV - All patients included in the study have completed the 12-month observation period.
 
The following will be carried out during the follow-up periods:
 

— Observation of MACCEs and collection of information about them;

— Monitoring and evaluation of the project;

— Observation and analysis of study activities, procedures, non-clinical outcomes and safety data.

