## 2.4.2 Expected Number of Study Participants

Patients with stable CAD who have undergone ePCI coronary artery stenting without clinically significant procedural complications, require conventional antiplatelet therapy with a P2Y12 inhibitor, meet inclusion criteria, do not present exclusion criteria, and provide informed consent for participation will be selected and randomized for the study.

The sample size of 240 study participants is determined for inclusion in the study. Calculations were made using two instruments that provided two approximate sample sizes. The median of these values (considering that the greater level of significance of the odds ratio and the relative absolute risk values could be achieved with the larger sample size) was taken as the sample size.

(1) Calculate the sample size for scientific studies using a standard numerator based on the proportion of the population that is likely to have the demographic characteristics of the study sample and the size (number) of the population with the clinical characteristics expected for the study, with a 95% confidence level and a  $\pm 5\%$  confidence interval for the results of the statistical calculations.

(2) Sample size calculation for a randomized, parallel case-control study with a two-sided statistical significance level, at a confidence interval of  $\alpha = 0.05$ , at statistical power of  $(1-\beta) = 0.8$ , at case/control ratio of 2, at probability of occurrence of an event in the experimental arm of  $p_0$  – up to 0.4, and at probability of occurrence of an event in the control arm of  $p_1$  – up to 0.6.

Study participants will be randomly assigned to two parallel groups, control and experimental, with a 1:2 allocation ratio and selected 3 study arms for participants by CYP2C19 genotyping results:

1st arm – experimental: "Normal Metabolizers of Clopidogrel", 110 study participants diagnosed with chronic coronary artery disease who had undergone elective PCI, tested with CYP2C19 genotyping and identified as NFA \*2, \*3 carriers, who undergo CYP2C19 Genotype-Guided Clopidogrel Treatment - Clopidogrel as a component of preventive antiplatelet treatment such as double antiplatelet treatment (DAPT), or an antiplatelet drug (clopidogrel) combined with the non-vitamin K antagonist oral anticoagulants (NOAC), incl. triple antiplatelet treatment (Aspirin, Clopidogrel and a NOAC), or antiplatelet monotherapy (Clopidogrel).

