2nd arm - experimental: "Passive Metabolizers of Clopidogrel", approximately† 50 study participants diagnosed with chronic coronary artery disease who had undergone elective PCI, tested with CYP2C19 genotyping, identified as LOF \*2, \*3 allele carriers, who undergo CYP2C19 Genotype Guided Antiplatelet Treatment Alternative to Clopidogrel - an antiplatelet drug alternative to clopidogrel in conventional dosing regimen, as a component of preventive antiplatelet treatment, such as double antiplatelet treatment (DAPT) with ticagrelor or prasugrel, or prasugrel combined with the nonvitamin K antagonist oral anticoagulants (NOAC), or antiplatelet monotherapy (ticagrelor, or prasugrel).

3rd arm - active comparator: "Unspecified Metabolizers of Clopidogrel", 80 participants diagnosed with chronic coronary artery disease who had undergone elective PCI were allocated to the arm, without CYP2C19 genotyping through simple randomization, and having an unspecified metabolism phenotype, who were assigned to the conventional clopidogrel treatment - clopidogrel as a component of preventive antiplatelet treatment, such as double antiplatelet treatment (DAPT), or clopidogrel combined with the non-vitamin K antagonist oral anticoagulants (NOAC), incl. triple antiplatelet treatment (Aspirin, Clopidogrel and a NOAC), or antiplatelet monotherapy (Clopidogrel).

† The prevalence of carriers of CYP2C19 \*2, \*3 non-functional alleles in the Georgian population has not been studied and is unknown. To estimate the number of patients in subgroup II arm 1 and arm 2, we used the extrapolation of known data from a European population study [12].

2 study arms could be used as control for analyzing and comparing study outcome measures: 3rd study arm participants create the active comparators' group for 1st and 2nd arm, and besides, 2nd study arm participants - as the comparators for 1st arm:

Control 1: "Normal Metabolizers of Clopidogrel" - 110 study participants vs "Unspecified Metabolizers of Clopidogrel" - 80 participants;

Control 2: "Passive Metabolizers of Clopidogrel" - approximately 50 participants vs "Unspecified Metabolizers of Clopidogrel" - 80 participants;

Control 3: "Normal Metabolizers of Clopidogrel" - 110 study participants vs "Passive Metabolizers of Clopidogrel" - approximately 50 participants.

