## **2.5.9 Processing of Biological Study Material**

As part of the study, blood samples from study participants will be processed for CYP2C19 genotyping. In addition, during the observation period, study subjects may undergo routine clinical tests by processing blood and urine samples.

Laboratory testing for CYP2C19 genotyping should be performed on at least 160 patients randomized to the study treatment arm for clopidogrel or an alternative P2Y12 inhibitor treatment intervention and for allocation to the appropriate study arm. Blood samples will be processed for this analysis only once during the study period.

The sample laboratory examination for CYP2C19 \*2, \*3 allele genotyping will be carried out in the Ltd "Vistamedi" diagnostic laboratory.

The analysis requires a 3 ml venous blood sample, obtained by simple venipuncture manipulation. The blood sample will be collected at the research center. The blood sample is immediately placed in a K3 EDTA type tube.

The tube label must be marked with the patient's unique number in the study. Along with the blood sample preparation, a sample form (paper) must be filled out, accompanying the sample during transportation to the laboratory. The sample form must include:

- The patient's unique number or code in the current study;
- The sample tube number (or the tube barcode must be marked).
- Sample volume;
- Purpose of the sample, name of the test.
- Place of sample collection;
- Time of sample collection;
- Time of sample shipment;
- Method of transportation;

The sample should be transported to the laboratory in a special blood sample transport container that ensures compliance with the transportation temperature (from -20° to -80°) regime.

Upon receipt in the laboratory, the sample with the accompanying form will be stored in a storage space (refrigerator) with a temperature regime from -20° to -80°, accessible to authorized study personnel.

The obtained sample will be subjected to analysis for CYP2C19 \*2, \*3 allele genotyping using the RT-PCR-based allele discrimination method. The analytical procedures include the stages of DNA extraction from the obtained blood sample, pre-PCR and PCR, which are performed using DNA extraction reagents and appropriate primers. Appendix 2 presents the main procedural descriptions of the analytical phase of CYP2C19 \*2, \*3 allele genotyping that should be applied in the study.

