### **2.6.3 Statistical Analysis of Study Results**

Primary statistical analysis will be carried out using descriptive statistics methods. The values and distribution of quantitative and qualitative variables from the study participants' initial clinical assessment and follow-up results will be evaluated according to the experimental and control arms. The magnitudes and trends of the variations of the data values will be analyzed.

Quantitative variable data will be calculated by mean, standard deviation, and median. For comparative statistical analysis, differences between the variable values will be calculated using the t-test or the Wilcoxon signed-rank test.

Categorical variable data will be calculated as frequencies and percentages (%). For comparative statistical analysis, differences between the variable values will be calculated using the chi-square or Fisher's exact tests.

To analyze the effectiveness of selected study interventions, the frequency of detection of clinical endpoints in the experimental treatment intervention arms (Rt1 and Rt2) and the comparator arm (Rc) will be calculated. According to the frequencies of clinical endpoint-positive and -negative cases detected in the study arm, the odds ratio (OR), hazard ratio - Cox proportional hazards regression (HR), relative risk (RR), relative benefit (RB) and absolute benefit (AB) indicators at 95%CI will be calculated.

The obtained results and indicators of treatment intervention effectiveness will be selected to consider the applicability of the study findings and the possibility of the study results translation into real-world clinical practice.

Data evaluation will be carried out continuously, immediately after they enter the registration form and the database. Preliminary statistical calculations and analysis for study evaluation and monitoring will be provided in several stages, when:

I - More than 50% of patients will be included in the study;

II - The study arms will be fully formed, and more than 50% of patients will complete a 3-month and a 6-month follow-up;

III - All study participants will be included in the study, and at a minimum, half of them will complete a 6-month and a 12-month observation period;

IV - All study participants included in the study will complete a 12-month follow-up.

The development of clinical endpoints will be monitored, and the relevant data will be collected in a special data registration form.

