
The relative risk (RR) of repeated non-adherence to medication treatment for aggregated 'normal metabolizer' and 'passive metabolizer' study participants' arms vs 'unspecified metabolizer' study participants' arm
	
Numerator: probability of the repeated non-adherence to medication treatment in the aggregated 'normal metabolizer' and 'passive metabolizer' study participants arm, calculated as the aggregated number of 'normal metabolizer' and 'passive metabolizer' study participants with repeated non-adherence to medication treatment divided on the sum of aggregated number of 'normal metabolizer' and 'passive metabolizer' study participants with repeated non-adherence to medication treatment and aggregated number of 'normal metabolizer' and 'passive metabolizer' study participants without repeated non-adherence to medication treatment;
 
Denominator: probability of repeated non-adherence to medication treatment in the 'unspecified metabolizer' study participants' arm, calculated as the number of 'unspecified metabolizer' study participants with repeated non-adherence to medication treatment divided by the sum of the number of 'unspecified metabolizer' study participants with repeated non-adherence to medication treatment and the number of 'unspecified metabolizer' study participants without repeated non-adherence to medication treatment;

Costs associated with the utilization of medical care services of real-world clinical practice in the study cases (in USD, <math>m \pm Std</math>)
	
Calculating: Mean value of the costs (<math>m</math>) and standard deviation (<math>Std</math>) in the 95% confidence interval

Costs associated with the utilization of medical care services of real-world clinical practice in the 'normal metabolizer' study arm cases (in USD, <math>m \pm Std</math>)
	
Calculating: Mean value of the costs (<math>m</math>) and standard deviation (<math>Std</math>) in the 95% confidence interval

Costs associated with the utilization of medical care services of real-world clinical practice in the 'passive metabolizer' study arm cases (in USD, <math>m \pm Std</math>)
	
Calculating: Mean value of the costs (<math>m</math>) and standard deviation (<math>Std</math>) in the 95% confidence interval

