
Costs associated with the utilization of medical care services of real-world clinical practice in the 'unspecified metabolizer' study arm cases (in USD, <math>m \pm Std</math>)
	
Calculating: Mean value of the costs (<math>m</math>) and standard deviation (<math>Std</math>) in the 95% confidence interval

Difference in costs associated with the utilization of medical care services of real-world clinical practice between 'normal metabolizer' study participants' arm vs 'unspecified metabolizer' study participants' arm
	
Measuring: Statistical significance of the difference between the means two study arms in the 95% confidence interval by <math>p</math> value using Student's Two-sample t-test

Difference in costs associated with the utilization of medical care services of real-world clinical practice between aggregated 'normal metabolizer' and 'passive metabolizer' study participants' arms vs 'unspecified metabolizer' study participants' arm
	
Measuring: Statistical significance of the difference between the means two study arms in the 95% confidence interval by <math>p</math> value using Student's Two-sample t-test

Incremental costs associated with the utilization of medical care services of real-world clinical practice in the study cases manifested MACCEs (in USD, <math>m \pm Std</math>)	Calculating: Mean value of the costs ( $m$ ) and standard deviation ( $Std$ ) in the 95% confidence interval
Incremental costs associated with the utilization of medical care services of real-world clinical practice in the 'normal metabolizer' study arm cases manifested MACCEs (in USD, <math>m \pm Std</math>)	Calculating: Mean value of the costs ( $m$ ) and standard deviation ( $Std$ ) in the 95% confidence interval
Incremental costs associated with the utilization of medical care services of real-world clinical practice in the 'passive metabolizer' study arm cases manifested MACCEs (in USD, <math>m \pm Std</math>)	Calculating: Mean value of the costs ( $m$ ) and standard deviation ( $Std$ ) in the 95% confidence interval
Incremental costs associated with the utilization of medical care services of real-world clinical practice in the 'unspecified metabolizer' study arm cases manifested MACCEs (in USD, <math>m \pm Std</math>)	Calculating: Mean value of the costs ( $m$ ) and standard deviation ( $Std$ ) in the 95% confidence interval

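### Costs are compared with Student's t-test between unequal groups (110 v 80 and about 160 v 80); if cost spread differs by arm, the two overall cost comparisons miss the nominal 5%, in a direction that cannot be known in advance

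*Combined protocol and SAP*

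**What the plan says.** The cost rows at the end of Appendix 3 contain eight comparisons. There are two contrasts: normal metabolizers against the unspecified arm, and normal plus passive metabolizers against the unspecified arm. Each is made once for all participants and once each for cases with MACCE, MACE or NACE. All eight are to be judged by a p "value using Student's Two-sample t-test".

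The cost summary rows ask for the mean and the "standard deviation ( Std ) in the 95% confidence interval".

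Section 2.6.3 says of quantitative variables in general that "differences between the variable values will be calculated using the t-test or the Wilcoxon signed-rank test". No unequal-variance test, bootstrap, transformation or check of spread is planned for costs.

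Section 2.4.2 sets the first contrast at "110 study participants vs 'Unspecified Metabolizers of Clopidogrel' - 80 participants". For the second, section 2.4.2 adds about 50 passive metabolizers to the 110, and section 2.5.9 says that genotyping "should be performed on at least 160 patients randomized to the study treatment arm". The control arm stays at 80.

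Costs appear in the Synopsis among the other end-points. They are neither primary nor secondary.

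**The concern.** Student's test estimates one common variance, weighted towards the larger group. With unequal groups, if the smaller group has the larger spread, the standard error comes out too small and the test rejects too often. If the larger group has the larger spread, the reverse happens.

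Unequal cost spread is plausible here. The aggregated guided group mixes clopidogrel with ticagrelor or prasugrel, while the control arm uses clopidogrel only. In addition, an arm with more events carries more expensive care. These two influences need not point the same way.

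Section 2.6.3 offers no way out: the signed-rank test is a paired test and does not fit independent arms.

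At stake is whether a reported cost difference, or its absence, has the error rate and interval coverage it claims.

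**Working it through.** **Inputs from the documents.** Groups are 110 v 80, and 110 + about 50 = 160 v 80. The sample-size calculation is two-sided with α = 0.05 (Synopsis), "at case/control ratio of 2". No SD, expected difference or power is stated for costs.

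**The nearest figure in the plan.** Section 2.6.2, calculation (2), gives a minimum of 221 for a binary event at 0.4 v 0.6 with 80% power. The control group needs n = [1.960·√(1.5 × 0.4667 × 0.5333) + 0.8416·√(0.24 + 0.24/2)]² / 0.2² = (1.1976 + 0.5050)² / 0.04 = 72.5, so 73. The total is 73 + 146 = 219, within 2 of the stated figure. This confirms the 2:1 design and says nothing about costs.

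**Assumption.** The ratio of control SD to guided SD is varied, with equal mean cost in both groups.

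**Formulas.**
- Pooled variance: sp² = [(n₁−1)s₁² + (n₂−1)s₂²] / (n₁+n₂−2)
- Standard error used by the test: SEp = √[sp²(1/n₁ + 1/n₂)]
- True standard error: SEt = √(s₁²/n₁ + s₂²/n₂)
- True two-sided error: 2[1 − Φ(t_crit × SEp/SEt)]

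**Worked case: 160 v 80, guided SD 1, control SD 2.**
- sp² = (159 × 1 + 79 × 4)/238 = 1.996
- SEp = √(1.996 × 0.01875) = 0.1934
- SEt = √(1/160 + 4/80) = 0.2372
- SEp/SEt = 0.816, so the interval is 18% too narrow
- t_crit = 1.970; 1.970 × 0.816 = 1.607; true error 10.8%

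| Groups (guided v control) | Control SD : guided SD | SEp/SEt | True two-sided error |
|---|---|---|---|
| 160 v 80 | 1 : 1 | 1.000 | 5.0% |
| 160 v 80 | 1.5 : 1 | 0.879 | 8.4% |
| 160 v 80 | 2 : 1 | 0.816 | 10.8% |
| 160 v 80 | 1 : 2 | 1.226 | 1.6% |
| 110 v 80 | 2 : 1 | 0.909 | 7.3% |
| 110 v 80 | 1 : 2 | 1.100 | 3.0% |

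Using 1.96 in place of t_crit moves these by at most 0.2 points (for example 11.0% instead of 10.8%). Simulation with normal costs, 40,000 runs per case, agrees: 11.4% and 1.7% for the twofold ratios at 160 v 80. Welch's test stayed between 4.8% and 5.3% throughout. At the 75% completion assumed in section 2.4.2 (120 v 60, about 82 v 60) the results hardly change.

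**Skewed costs.** With lognormal costs of equal mean, 160 v 80:
- coefficient of variation 0.75 guided and 1.5 control: Student 11.4%, Welch 7.9%
- the reverse: Student 3.0%, Welch 4.9%
- coefficient of variation 1 guided and 2 control: Student 11.3%, Welch 9.3%

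Welch is closer to 5% in each of these cases but does not fully restore it when the smaller group is the more skewed.

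**Event-only rows.** Section 3.2.1 puts MACCE at 1–10%. The aggregated MACCE comparison would then hold 160 × 0.01 = 1.6 to 160 × 0.10 = 16 people against 80 × 0.01 = 0.8 to 80 × 0.10 = 8, that is about 2–16 v 1–8. The 160 v 80 and 110 v 80 results above do not describe these rows.

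**SD label.** The half-width of m ± SD is SD; that of a 95% CI of the mean is t × SD/√n. Their ratio is √n/t, which is 4.5 at n = 80, 5.3 at n = 110 and 6.4 at n = 160. This holds whatever the spread in the other arm.

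**The case against.** The strongest reply is that nothing in the documents shows the spread to be unequal. The two reasons for expecting it can pull in opposite directions: mixed drugs widen the guided group, and more events widen whichever arm has them. Suppose cost spread came only from events at a fixed cost each. The SD ratio would be √[pc(1−pc)/(pg(1−pg))], where pc and pg are the control and guided event probabilities. At the sample-size rates of 0.6 and 0.4 that is exactly 1, with no distortion. At an assumed 10% v 5% it is √(0.09/0.0475) = 1.38, giving 7.6% for 160 v 80 and 6.1% for 110 v 80. A ratio near 2 needs roughly a fourfold difference (10% v 2.5% gives 1.92). An arm with more costly events would usually also have a higher mean, so a doubled SD with equal means is an unfavourable case.

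This stands. It makes the point conditional and modest for 110 v 80. It does not support Student's test, because Welch loses almost nothing when the spreads are equal.

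It is also fair that equal variance is nowhere written; it is inferred from the name of the test. If the software run under that name did not pool, the point about the test would fall away. The plan should then say so.

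The small numbers in the MACCE rows rest on the 1–10% of section 3.2.1. If the 0.4 and 0.6 of section 2.6.2 applied to MACCE instead, those rows would hold 160 × 0.4 = 64 v 80 × 0.6 = 48. No frequency is given for MACE or NACE. Selection on an event after randomisation affects all six rows at any frequency.

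Finally, the row titles already specify mean ± SD, so the SD label may be no more than awkward wording for mean, SD and a 95% CI.

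**Conclusion.** The point holds conditionally. Student's test between groups of 160 v 80 has a true error of 5% at equal spread, about 8.4% to 10.8% if the control SD is 1.5 to 2 times the guided SD, and about 1.6% if the guided SD is twice the control SD. At 110 v 80 a twofold ratio gives 7.3% or 3.0%. These figures rest on the pooled reading of the test, on assumed SD ratios and on equal means. They apply to two of the eight cost comparisons.

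A reader might infer that the cost p-values are simply wrong, or that they lean towards declaring a difference. The documents do not support either: with no cost SDs, neither the size nor the direction of the departure is known. A reader might also infer that the phrase "in the 95% confidence interval" attached to the SD distorts the tests. It does not: it is a separate reporting defect and touches no p-value.

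This is a free improvement, limited to an 'other' end-point. No primary or secondary conclusion depends on it.

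**What to change.** In Appendix 3:

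- **Two overall cost comparisons.** Replace Student's test with Welch's unequal-variance test, and report the difference in mean cost with a bootstrap 95% CI. The bootstrap is added because Welch alone stays somewhat above 5% under strong skew; its own coverage was not simulated here.
- **Six comparisons among MACCE, MACE or NACE cases.** Report them descriptively, without p-values.
- **Cost summary rows.** Report the SD as an SD, and give the 95% CI of the mean as a separate figure.

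The cost is a few edited lines in Appendix 3, one software option for Welch and a short bootstrap routine. No change to data collection, visits or sample size is needed.
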